#### 12.4 Analysis Datasets

Population	Definition
Enrolled	This will comprise all subjects who meet the eligibility criteria and are registered onto the study.
Evaluable	Subjects who receive at least one dose of trial drug TAK-228 and have at least one response assessment or die before any evaluation.
Safety	All subjects receiving at least one dose of TAK-228 will be included in analysis unless otherwise specified.

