#### 5.3 Subject Evaluations

Subjects will be evaluated clinically every week for Cycle 1, every 2 weeks for Cycles 2-3, and then every 4 weeks for subsequent cycles. On the days that a subject is seen in clinic, subjects are not required to physically dose in clinic. There is no in-clinic dosing requirement.

Subjects will undergo disease assessments with imaging every 8 weeks relative to the C1D1 visit and continue on study therapy until radiographic progression, unacceptable toxicity or withdrawal.

Subjects that do not have archived tissue from the previous 18 months available will undergo one mandatory biopsy at screening. The pretreatment biopsy must occur within 28-days prior to initiation of therapy. In subjects who have an objective disease response as per RECIST version 1.1 and then subsequently progress, a second biopsy at time of progression will be mandatory if feasible and safe. Subjects should continue study treatment until the day prior to the progression biopsy. Progression biopsy must occur within 28-days of determination of disease progression.

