### **12.2 Endpoints**

#### **12.2.1 Definition of Primary Endpoint**

Objective Response (OR): Confirmed CR or PR as best overall response according to RECIST version 1.1 by central review. Objective response will be determined by the best overall confirmed response designation recorded between the date of first dose of trial therapy and the date of objectively documented disease progression or cessation of trial therapy, whichever occurs first. For subjects without documented progression or cessation of trial therapy, all available response designations will contribute to the objective response determination.

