### **12.3 Sample Size and Accrual**

Forty subjects with metastatic RCC will be enrolled for a goal of 38 evaluable subjects (assuming 5% not evaluable). The two-stage single arm phase II study is designed to detect an improvement in response rate from 5% to 20%. Assuming a type I error of 0.05 and targeting 90% statistical power, 20 patients will be accrued (for 19 evaluable) in the first stage. The first interim analysis will occur when the first 8 week imaging assessment for response data is available for all 20

patients. If 1 or more responses are observed, the accrual will continue to the second stage. Twenty (for 19 evaluable) additional patients will be accrued in the second stage. TAK-228 will be declared ineffective in this study if <5 responses are observed. It will be considered worthy of further study if more than 4 ( $\geq 5$ ) responses are observed.

The design operating characteristics are as follows:

Hypothesis	#s responses at stage I	Prob(stop at first stage)	Overall # responses	Prob(Rx declared inactive)	Design Statistics
Ho: ORR=0.05	<1	38%	$\leq 4$	96%	True type I error 0.04
Ha: ORR=0.2	<1	1.4%	$\leq 4$	10%	Power: 90%

The 90% confidence intervals for the response rate in a two-stage phase II design are summarized as below. The calculation employed the method of Atkinson and Brown (1985) *Biometrics* 741-744

Observed # of responses	Response rate	90% CI
4/38	0.105	(0.04, 0.23)
5/38	0.13	(0.05, 0.26)
6/38	0.16	(0.07, 0.29)
7/38	0.18	(0.09, 0.32)

The accrual is expected to be 3 subjects every month for 14 months to complete enrollment with additional follow-up to 2 years for disease progression or survival. The study is expected to last approximately 40 months.

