#### **12.4.1 Analysis Plans for Primary Objective**

ORR is defined as the proportion of subjects who achieve objective response, as defined in Section 12.2.1. ORR and its 90% exact confidence interval (CI) using the method of Atkinson and Brown (1985) will be provided based on the evaluable population. Best overall response (BOR) will also be summarized. In addition, tumor burden data will be summarized by waterfall plot showing the maximum tumor shrinkage and spider plot showing individual subject tumor burden over time.

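### The primary ORR uses an evaluable set that leaves out some treated subjects who cannot be responders, so it can only equal or exceed the all-treated ORR; the shift is small and the go/no-go decision is unaffected

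*Combined protocol and SAP*

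**What the plan says.** - **Population for the primary analysis.** Section 12.4.1 states that the ORR and its exact 90% CI "will be provided based on the evaluable population". Section 12.4 defines that population as "Subjects who receive at least one dose of trial drug TAK-228 and have at least one response assessment or die before any evaluation".
- **Other sets in Section 12.4.** The Enrolled set: "This will comprise all subjects who meet the eligibility criteria and are registered onto the study". The Safety set: "All subjects receiving at least one dose of TAK-228 will be included in analysis unless otherwise specified". Neither is assigned to the ORR.
- **Responder.** Section 12.2.1 requires "Confirmed CR or PR as best overall response according to RECIST version 1.1 by central review". The response must be recorded between first dose and "the date of objectively documented disease progression or cessation of trial therapy, whichever occurs first".
- **Planned loss.** Section 12.3: "Forty subjects with metastatic RCC will be enrolled for a goal of 38 evaluable subjects (assuming 5% not evaluable"). It does not say why 5% would be non-evaluable.
- **Decision rule.** Section 12.3 continues to stage 2 with at least 1 response in stage 1 and calls the drug promising with at least 5 responses overall.
- **Timing of scans.** Section 5.3: "Subjects will undergo disease assessments with imaging every 8 weeks relative to the C1D1 visit". Neither the study calendar nor Section 7.3 schedules imaging at the treatment discontinuation visit.
- **Dropouts.** Section 5.8 does not replace them. Sections 4.1 and 4.3 cancel the registration of anyone never treated.

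**The concern.** The first on-treatment scan falls at week 8, and Section 5.5 lets subjects stop therapy before then for adverse events or by their own choice. Such a subject is in the Safety set. Without a later scan, and unless counted as a death before evaluation, the subject is not in the ORR denominator. Nothing in the plan adds these subjects back as non-responders, and no all-treated ORR is planned.

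The omission works in one direction only. The excluded subjects contribute nothing to the numerator, so removing them can only leave the ORR unchanged or raise it. They may include people who tolerate the drug poorly. At stake are the primary estimate and its interval, which readers will set against the 5% and 20% of Section 12.3.

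**Working it through.** **Inputs.** From Section 12.3: 40 enrolled, 38 evaluable, stages of 20 (19 evaluable) each, rates 5% and 20%, cut-offs of at least 1 and then at least 5 responses. From Section 12.4.1: 90% two-stage exact CI.

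**1. Reproduce the plan on 19+19.** With X1 and X2 the stage counts, P(stop) = (1−p)^19, and P(positive) is the sum over x1 ≥ 1 of P(X1 = x1) × P(X2 ≥ 5 − x1).
- p = 0.05: P(stop) = 0.377, P(positive) = 0.0390 (plan: 38%, 0.04).
- p = 0.20: P(stop) = 0.0144, P(positive) = 0.8967 (plan: 1.4%, 90%).

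For the interval at s responses, the lower limit solves P(continue and total ≥ s) = 0.05. The upper limit solves 1 − P(continue and total ≥ s+1) = 0.05. For 4 to 7 responses this gives the table in Section 12.3 after rounding.

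**2. Direction.** If a share w of treated subjects is excluded, the numerator is the same and

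reported ORR = all-treated ORR × 1/(1 − w).

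This is never below the all-treated ORR.

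**3. Size at the planned rate.** Take both non-evaluable subjects as dosed, unassessed and not counted as early deaths, so w = 2/40 = 5%.

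| Responses | Evaluable, 19+19 (90% CI) | All treated, 20+20 (90% CI) | Gap, points |
|---|---|---|---|
| 4 | 10.5% (3.7–22.7%) | 10.0% (3.5–21.7%) | 0.53 |
| 5 | 13.2% (5.4–25.8%) | 12.5% (5.1–24.6%) | 0.66 |
| 6 | 15.8% (7.1–28.8%) | 15.0% (6.8–27.5%) | 0.79 |
| 7 | 18.4% (9.0–31.8%) | 17.5% (8.5–30.4%) | 0.92 |
| 8 | 21.1% (10.9–34.8%) | 20.0% (10.4–33.2%) | 1.05 |

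**4. Range at 5 responses.**
- One of the two never dosed: 5/38 − 5/39 = 13.16% − 12.82% = 0.34 points. Neither dosed: zero.
- Assumed higher exclusion among 40 treated (rates not in the documents): w = 10% gives 5/36 = 13.9% (5.7–27.1%), a gap of 1.39 points; w = 15% gives 5/34 = 14.7% (6.0–28.6%), a gap of 2.21 points.

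**5. Decision.** The rule uses counts, so the denominator does not enter. As a check, take 20+20 treated, each assessed with probability 0.95. With 20% responding among the assessed (0.95 × 0.20 = 0.19 per treated subject), P(positive) is 0.8952 whether summed over the assessed or over all treated. With 5% among the assessed it is 0.0392 either way.

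**6. If 5% and 20% are read as all-treated rates.** The same cut-offs on 20+20 give type I error 0.0471 and power 0.920, within the stated 0.05 and 90%.

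**The case against.** The strongest reply is that the population is fixed in advance, named for the primary analysis and used to size and tabulate the design, so Sections 12.3 to 12.4.1 agree with each other. That stands: this is a choice of population, and a reader who infers a contradiction would be wrong.

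It would also be too strong to say that every treated subject who leaves alive before a scan is excluded. Three features narrow the gap:
- The provision for deaths before evaluation has no time limit. Sections 5.6 and 7.4 follow survival for up to 2 years, so a subject who leaves unassessed and dies in follow-up could be read as evaluable.
- Section 12.4 does not require the assessment to be on treatment. A scan after stopping brings the subject into the denominator, as a non-responder.
- Scans continue through toxicity holds (study calendar, footnote 8), the note to Table 17 asks for progression to be documented after discontinuation, and Section 12.3 times the interim for when 8-week imaging is available on all 20 stage 1 patients.

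These limit the gap but do not close it, since none guarantees a scan or a recorded death for each early leaver.

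A reader might also infer from the one-cycle condition in Section 9.1 that early deaths are dropped. Section 12.4 keeps them, and it is the section that defines the analysis populations.

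Finally, a reader could divide the response count by the size of the Safety set. That is true, but the plan does not commit to presenting that figure, and a denominator is better settled before the data are seen.

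**Conclusion.** The point holds, at minor severity. The direction is certain from Sections 12.2.1, 12.4 and 12.4.1. At 5 responses the gap is at most 0.66 points at the planned 5% loss, against an interval about 20 points wide (25.8 − 5.4 = 20.4). That maximum assumes both non-evaluable subjects were dosed, never assessed and not counted as early deaths. Cancelling never-treated registrations makes dosing plausible, but Section 12.3 does not state it. The gap shrinks if any of these conditions fails and grows if more than 5% leave unassessed; the plan sets no ceiling on that share.

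A reader might infer that the go/no-go decision is biased or the type I error inflated. The documents do not support this, because the rule in Section 12.3 counts responses. Only the reported estimate and interval are affected.

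**What to change.** In Section 12.4.1:
- Report the ORR and its two-stage 90% CI for all subjects with at least one dose (the Safety set already defined in Section 12.4). Count anyone without a confirmed response, including the unassessed, as a non-responder.
- Compute the interval for the number actually treated in each stage.
- Keep the Section 12.4 evaluable set as a sensitivity analysis.
- State how many treated subjects had no response assessment, and why.

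Keep the cut-offs of at least 1 and then at least 5 responses. If 5% and 20% are to be read as all-treated rates, restate the operating characteristics in Section 12.3 for 20+20 treated (type I error 0.047, power 0.920).

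The cost is wording and tables in Sections 12.3 and 12.4.1 and a slightly lower reported ORR. No patients are added.

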#### **12.4.1 Analysis Plans for Primary Objective**

ORR is defined as the proportion of subjects who achieve objective response, as defined in Section 12.2.1. ORR and its 90% exact confidence interval (CI) using the method of Atkinson and Brown (1985) will be provided based on the evaluable population. Best overall response (BOR) will also be summarized. In addition, tumor burden data will be summarized by waterfall plot showing the maximum tumor shrinkage and spider plot showing individual subject tumor burden over time.

#### **12.4.2 Analysis Plans for Secondary Objectives**

**Safety and Tolerability:** All adverse events recorded during the trial will be summarized for the safety population. The incidence of events that are new or worsening from the time of first dose of treatment will be summarized according to system organ class and/or preferred term, severity (based on CTCAE version 4.0 grade), type of adverse event, and relation to study treatment. Deaths reportable as SAEs and non-fatal serious adverse events will be listed by subject and tabulated by primary system organ class, and type of adverse event.

**PFS and OS:** PFS and OS will each be summarized using the product-limit method of Kaplan-Meier. Median times for each endpoint will be presented with two-sided 90% confidence intervals estimated using log(-log(survival)) methodology. Kaplan-Meier estimates of PFS at 6 or 12 months after treatment initiation may also be presented with two-sided 90% confidence intervals.

#### **12.4.3 Analysis Plans for Exploratory Objectives**

It's expected that 80% of the trial samples will have adequate specimens for the correlative study and the evaluable samples for the correlative analyses will be 32 (80% of 40 subjects).

A DFCI mutation screen analysis of 300 cancer genes (Oncopanel), including all those involved in regulation of mTOR, will be performed on pre-treatment biopsies in all subjects.

The mutation profiling will be performed using next generation sequencing via Oncopanel in all cases and whole exome sequencing in a subset of subjects.

The sample size/power justification is focused on the primary objective of assessing the association between ORR and mTOR pathway mutation status (defined as mutation(s) observed in 1 gene or several genes belonging to mTOR pathways). To examine the response (or ORR) by the mutation status (mutated or non-mutated), the evaluable samples will be divided retrospectively according to objective response or non-response. Pre-treatment mutation status will be summarized descriptively for the response/non-response groups.

The trial's targeted ORR rate was 0.2. Based on our experience (submitted for publication) the mutation rate for a cohort of mRCC subjects treated with mTOR inhibitors was 20% (16/79), we assumed a mTOR pathway gene mutations rate of 0.25 for the power estimation, as it is suggested that "23-38% of subjects likely have alteration in the mTOR pathway.

With an evaluable correlative sample size of 32, the study has 80% power to detect a 48% increase (one-sided  $\alpha=0.05$ ) in response probability of 56% in subjects with mutations as compared to that of 8% in subjects without mutations.

The proportion of subjects with objective response according to pre-treatment (baseline) mutation status will also be summarized with two-sided 90% exact binomial CI. Kaplan-Meier estimates will be used to assess the distribution of PFS according to mutation status. Medians of time to PFS will be shown with two-sided 90% CIs.

## **12.5 Interim Analysis/Criteria for Stopping Study**

There are no formal interim efficacy analyses planned for this study.

## **13. DATA REPORTING/REGULATORY REQUIREMENTS**

Adverse event lists, guidelines, and instructions for AE reporting can be found in Section 11 (Adverse Events)

### **13.1 Data Reporting**

#### **13.1.1 Method**

The Office of Data Quality (ODQ) will collect, manage, and perform quality checks on the data for this study.

#### **13.1.2 Responsibility for Data Submission**

Investigative sites within DF/HCC or DF/PCC are responsible for submitting data and/or data forms to the Office of Data Quality in accordance with DF/HCC SOPs.

### **13.2 Data Safety Monitoring**

The DF/HCC Data and Safety Monitoring Committee (DSMC) will review and monitor toxicity and accrual data from this study. The committee is composed of clinical specialists with experience in oncology and who have no direct relationship with the study. Information that raises any questions about participant safety will be addressed with the Overall PI and study team.

The DSMC will review each protocol up to four times a year or more often if required to review toxicity and accrual data. Information to be provided to the committee may include: up-to-date participant accrual; current dose level information; DLT information; all grade 2 or higher unexpected adverse events that have been reported; summary of all deaths occurring within 30 days of intervention for Phase I or II protocols; for gene therapy protocols, summary of all deaths while being treated and during active follow-up; any response information; audit results, and a

summary provided by the study team. Other information (e.g. scans, laboratory values) will be provided upon request

### **13.3 Multicenter Guidelines**

This protocol will adhere to the policies and requirements of the DF/HCC Multi-Center Data and Safety Monitoring Plan. The specific responsibilities of the Overall PI, Coordinating Center, and Participating Institutions and the procedures for auditing are presented in Appendix E.

- The Overall PI/Coordinating Center is responsible for distributing all IND Action Letters or Safety Reports to all participating institutions for submission to their individual IRBs for action as required.
- Mechanisms will be in place to ensure quality assurance, protocol compliance, and adverse event reporting at each site.
- Except in very unusual circumstances, each participating institution will order the study agent(s) directly from supplier. A participating site may order the agent(s) only after the initial IRB approval for the site has been forwarded to the Coordinating Center.

### **13.4 Data Quality Oversight Activities**

Validation of data will be completed on a continual basis throughout the life cycle of the study. A summary report (QC Report) of these checks together with any queries resulting from manual review of the eCRFs will be generated for each site and transmitted to the site and the site monitor. Corrections will be made by the study site personnel.

There will be at least one routine visit per site per year for sites that have accrued. Additional for cause visits may occur as necessary. Source documents will be reviewed for verification of agreement with data entered into InForm. It is important for the site investigator and their relevant personnel to be available for a sufficient amount of time during the monitoring visits or audit, if applicable. The site investigator and institution guarantee access to source documents by the sponsor/investigator or its designee.

The trial site may also be subject to quality assurance audit by Millennium or its designee as well as inspection by appropriate regulatory agencies.

### **13.5 Compliance with Trial Registration and Results Posting Requirements**

Under the terms of the Food and Drug Administration Modernization Act (FDAMA) and the Food and Drug Administration Amendments Act (FDAAA), the sponsor-investigator of the trial is solely responsible for determining whether the trial and its results are subject to the requirements for submission to the Clinical Trials Data Bank, <http://www.clinicaltrials.gov>. All results of primary and secondary objectives must be posted to CT.gov within a year of

completion. Information posted will allow subjects to identify potentially appropriate trials for their disease conditions and pursue participation by calling a central contact number for further information on appropriate trial locations and study site contact information.

## **14. DATA HANDLING AND RECORD KEEPING**

### **14.1 Data Management**

The Dana-Farber Cancer Clinical Trials Office will provide Project Management and Monitoring services for this trial. Data will be collected through the web based clinical research platform, InForm , a system compliant with Good Clinical Practices and Federal Rules and Regulations created by the Clinical Trials Research Informatics Office (CTRIO). All data will be collected and entered into InForm by study site personnel from participating institutions.

### **14.2 Case Report Forms and Submission**

Generally, clinical data will be electronically captured in InForm and correlative results will be captured in spreadsheets or other secure database(s). If procedures on the study calendar are performed for standard of care, at minimum, that data will be captured in the source document. Select standard of care data will also be captured in InForm, according to study-specific objectives.

The completed dataset is the sole property of the sponsor-investigator's institution and should not be exported to third parties, except for authorized representatives of appropriate Health/Regulatory Authorities, without permission from the sponsor-investigator .

### **14.3 Record Retention**

To enable evaluations and/or audits from Health Authorities, the site investigator agrees to keep records, including the identity of all subjects (sufficient information to link records; e.g., hospital records), all original signed informed consent forms, copies of all source documents, and detailed records of drug disposition. All source documents are to remain in the subject's file and retained by the site investigator in compliance with the site contract. . No records will be destroyed until the sponsor/investigator confirms destruction is permitted.

#### **14.4 Confidentiality**

There is a slight risk of loss of confidentiality of subject information. All records identifying the subjects will be kept confidential and, to the extent permitted by the applicable laws and/or regulations, will not be made publicly available. Information collected will be maintained on secure, password protected electronic systems. Paper files that contain personal information will be kept in locked and secure locations only accessible to the study site personnel.

Subjects will be informed in writing that some organizations including the sponsor-investigator and his/her research associates, Millennium, IRB, or government agencies, like the FDA, may inspect their medical records to verify the information collected, and that all personal information made available for inspection will be handled in strictest confidence and in accordance with local data protection laws.

If the results of the study are published, the subject's identity will remain confidential.

#### **15. PUBLICATION PLAN**

The data will be collected by the investigators and analyzed by the co-principal investigators and the statistical team at DFCI. It is anticipated that the results will be made public within 12 months of the end of data collection. A report is planned to be published in a peer-reviewed journal, however initial release may be an abstract that meets the requirements of the International Committee of Medical Journal Editors. [REDACTED] in consultation with [REDACTED] [REDACTED] as well as outside investigators will decide on the authorship orders for abstracts and manuscripts from the trial.

